In the R61 phase, we will examine the impact of SING on computational behavioral metrics of (Aim 1) Conditioned Hallucinations, (Aim 2) Social Reinforcement Learning, (Aim 3) Language Use, in 50 participants with voice hearing in the context of a psychotic illness. Following a screening visit to determine eligibility, these computerized tasks will be administered behaviorally, and an interview will elicit speech, prior to and following the full SING intervention (in 10 groups of 5 participants, each facilitated by a trained musical interventionist, during the first two years of the project). If SING meaningfully alters these computational task parameters (decision criteria outlined below), we will proceed to the R33 phase, wherein we will recruit a further 200 voice hearing participants with similar diagnoses. These participants will complete the same

tasks deemed mechanistically relevant in the R61 phase, prior to and following randomization to four different conditions (facilitated by an interventionist musician) that will deconstruct the possible active ingredients of SING along two dimensions: Activity and Ownership: (a) SING (n=50, Activity + and Ownership +), participants produce and perform their own song; (b) Karaoke (n=50, Activity + and Ownership -), participants perform karaoke, singing along to others music; (c) Pop Music (n=50, Activity – and Ownership -), participants will listen to popular music chosen by the music interventionists; and (d) Curated Playlists (n=50, Activity -, Ownership +), participants will curate playlists of popular music and listen to them together. This deconstruction will provide insights into the predictive processing framework, as applied to hallucinations and music, specifically, whether changes at higher, a-modal, hierarchical levels, particularly sense of self and active inference, influence precision weighted perceptual and social inferences more so than inactive experiences or experiences that do not engage sense of self.

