SING Intervention (R61). A trained musician-facilitator will convene a series of four weekly two-hour sessions to which groups of five participants will be invited (total n=50 participants, or n=10 groups). The groups will be convened at the Connecticut Mental Health Center for convenience (though other locations may be employed). The facilitator provides keyboard, professional microphone, recording interface, headphones, guitar, computer and a Digital Audio Workstation (DAW) for recording. The first 10 minutes of group involve introductions to the other participants and facilitator as well as the goals of the session. Participants will be given paper and a pencil with which to brainstorm potential lyrics. The next 5 minutes involve body and vocal warm ups, listening to self and others. For the next 90 minutes, participants will work

together with the facilitator and independently to create their own original lyrics and melody. Each song will have at least one collaborative section (usually the chorus) where lyrics are written and performed together by the whole group. Participants also have the ability to write alone and perform sections by themselves. For the last 10 minutes, the group listens back to the entire song that they created. In the final 5 mins, the session is concluded, and the group disbands until the next session. Post-session, the facilitator notes level of contribution and any other significant points regarding individual participation and group coherence (these may be used to weight each participant's contributions to analyses of the intervention's impact on computational behavioral endpoints). Finally, we appreciate that it is crucial to provide continued opportunities for engagement with MI after the conclusion of the group, should the participants desire. In the final session, participants will be provided with information sheets on local studio opportunities, karaoke nights and other opportunities to produce, perform and experience music.

R61 Aim 1 Conditioned Hallucinations:

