R61 Statistical Power: Aims 1-3: Since all participants will perform all studies in Aims 1-3 (Conditioned Hallucinations, Social Learning and Linguistic Markers), we powered our study based on our own preliminary data. Estimated effects for our proposed study of the impact of SING on conditioned hallucinations model parameters are based upon our own data in **Figure 2**. If SING can curtail these group differences – i.e. decrease hallucinating patient responses to the level of non-hallucinating controls, then we would predict the true difference in HGF model parameters pre- versus post-SING would be 0.01 arbitrary units and the within-patient standard deviation of the parameter estimates would be 0.02. We will analyze the model parameter specific to each Aim using paired sample's t-tests, leveraging the added power of within-participant designs. We estimate we will need at least 31 participants to have 80% power to detect a treatment difference at a two-sided 0.05 significance level⁵⁴. We budgeted for 50 unique participants to allow for participant drop-out and the detection of smaller effects of SING on conditioned hallucination behavior, social learning and language use.

Go/No Go Decision: We powered the R61 phase in order to detect complete resolution of conditioned hallucination metrics to the level of non-hallucinating control participants. But we propose a much larger sample of participants in order to be powered to detect smaller changes in conditioned hallucination metrics, social learning and language use. Given standard pharmacotherapies for hallucinations are associated with residual symptoms in 30-50% of participants⁵⁵, it would seem an unfairly high bar to demand complete normalization of a candidate behavioral metric in order for an effect on that metric to be meaningful and solicitous of follow-up investigation. In the clinical trials literature, Jacobson and Truax⁵⁶ determining clinical significance is often used. It is defined as two standard deviations or greater change in the direction of symptomatic improvement following treatment. We propose to adopt this standard for each metric examined in each of Aims 1-3. **Conditioned Hallucination parameters, social learning rates or use of personal pronouns, biological words or negative emotional words change by two standard deviations or more from baseline pre-intervention, then those metrics will proceed to our R33 study. If no metrics meet that standard, we will not proceed with the R33.**

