		ACTIVE	
		-	+
OWNERSHIP	-	Listening (pop music) n=50	Karaoke (no recording) n=50
	+	Listening (curated playlists) n=50	SING (producing, performing) n=50

Figure 6. R33 Design

R33 Phase: Should we demonstrate a meaningful impact of SING on computational metrics of behavior, we will proceed to use those metrics in the R33 phase where we aim to deconstruct the active ingredients of SING along two key dimensions, Activity (whether engagement with the group is active or passive) and Ownership (creating some novel musical product, or not). Following screening, once participants have been deemed eligible, their behavior on the selected behavioral metrics will be assayed and they will be randomized to an intervention group. Performance on our computational metrics will be balanced across intervention groups prior to commencement of the four interventions (total n=200, n=50 per intervention, 10 groups of 5 participants per intervention):

- (1) **Passive Listening without Ownership** (Activity - / Ownership -, n=50). The group will meet on four occasions, once a week for two hours. The trained facilitator, having procured a playlist of popular music, will spend 15 minutes introducing the session, reminding participants not to sing along and to just sit quietly listening to the music. Next, the facilitator will play music from the playlist through a high-quality speaker at 60-75 decibels for 90 minutes. In the final 15 minutes, the facilitator will summarize the session and dismiss the participants, sharing follow-up music opportunities at the end of the fourth and final session.

- (2) **Passive Listening with Ownership** (Activity - / Ownership +, n=50). The trained facilitator will provide a computer and speaker with the ability to stream songs through many media outlets (i.e., Spotify, YouTube, Google). In the first fifteen minutes, the facilitator will introduce the session, participants are reminded not to sing along and to just sit quietly listening to the music. Next the participants will choose songs that they would like to hear. The list can be edited at any point. For the next 90 mins, the playlist will be played through a high-quality speaker at 60-75 decibels. In the final 15 minutes, the group will be concluded, and the participants will be dismissed. If it is the final session, they will be offered follow-up information about the musical opportunities.

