- (4) **SING** (Activity +/- Ownership +, n=50). As in the R61, the trained facilitator will provide a keyboard, professional microphone, recording interface, headphones, guitar, computer and a Digital Audio Workstation (DAW) for recording. The first 10 minutes of group involve introductions to the other participants and facilitator as well as the goals of the session. Participants will be given paper and a pencil with which to brainstorm potential lyrics. The next 5 minutes involve body and vocal warm ups, listening to self and others. For the next 90 minutes, participants will work together with the facilitator and independently to create their own original lyrics and melody. Each song will have at least one collaborative section (usually the chorus) where lyrics are written and performed together by the whole group. Participants also can write alone and perform sections by themselves. For the last 10 minutes, the group listens back to the entire song that they created. In the final 5 mins, the session is concluded, and the group disbands until the next session. If it is the final session, information sheets on local studio opportunities, karaoke nights and other opportunities to produce, perform and experience music.

For all four intervention types, at the end of each session, the facilitator notes level of contribution and any other significant points regarding individual participation and group coherence (these may be used to weight each participant's contributions to analyses of the intervention's impact on computational behavioral endpoints

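### Both phases treat people in groups of five, but the tests and the sample size of 31 assume independent participants, so p-values are too small if change is correlated within groups

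*Combined protocol and SAP*

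**What the plan says.** The Research Plan (Section I, item 4) delivers R61 "in 10 groups of 5 participants, each facilitated by a trained musical interventionist". The SING Intervention (R61) text describes "a series of four weekly two-hour sessions to which groups of five participants will be invited", so the same five people share the whole course. The R33 Phase text under Statistical Considerations (item 13) sets out "total n=200, n=50 per intervention, 10 groups of 5 participants per intervention". In SING, part of each song has "lyrics are written and performed together by the whole group". In the passive arm without ownership the facilitator begins by "reminding participants not to sing along and to just sit quietly listening to the music", and the curated-playlist arm carries a similar reminder.

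R61 Statistical Power names paired "t-tests, leveraging the added power of within-participant designs". It derives 31 participants from a pre-post difference of 0.01 and an SD of 0.02, then adds a margin: "We budgeted for 50 unique participants to allow for participant drop-out". R33 Power to Detect Effects names a 2x2 ANOVA on Activity and Ownership, and repeats the same inputs and the same 31.

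No section mentions a group effect, an ICC, a design effect or a cluster-robust variance. The facilitator's notes on participation and group coherence may be used to weight participants, but weighting does not model correlation between members of a group.

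**The concern.** People who spend four two-hour sessions together with one facilitator, and in SING write and perform a song jointly, may change in similar ways. A good or poor group then moves all five members. The paired t-test and the ANOVA would count those five as five independent pieces of evidence.

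The main exposure is R33. Its Activity and Ownership tests carry the conclusion about which ingredients of the intervention matter. With positive within-group correlation, false positives rise and power is overstated. The protocol also presents R33 as a built-in replication of R61; because both phases share the omission, agreement between them would not reveal it.

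A related gap is that the R33 figure of 31 is a one-sample pre-post number, whereas Activity and Ownership are comparisons between arms. That would need correcting even without groups. As things stand, no R33 power figure reflects either the arm contrast or the grouping.

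**Working it through.** **1. The plan's own figure.** Inputs from R61 Statistical Power: difference 0.01, SD 0.02, two-sided 5%, power 80%. Reading 0.02 as the SD of the paired difference:

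n = [0.02 × (1.960 + 0.842) / 0.01]² = 31.4

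This agrees with the stated 31 to within rounding (an exact t calculation gives 34). The formula assumes independent participants. The planning effect is 0.01/0.02 = 0.5 SD.

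**2. Error of the planned tests.** The ICC is not in the documents; 0.01, 0.05, 0.10 and 0.20 are assumed. With five per group, the variance of an arm mean is inflated by 1 + 4 × ICC. Averaged over the four arms, the Activity contrast is inflated by 1 + ICC if only SING groups are correlated, 1 + 2 × ICC if only the two active arms are, and 1 + 4 × ICC if all are. The true error is approximately 2 × [1 − Φ(1.96/√inflation)]. At ICC 0.05:

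- SING only: inflation 1.05, error 5.6%
- active arms only: 1.10, 6.2%
- all arms, and also R61: 1.20, 7.4%

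Simulation (10 groups of five per arm, change-score variance 1; 200,000 trials per cell for R61, 100,000 for R33) gave the following. Both planned tests held 5.0% at ICC 0.

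| Planned test, nominal 5% | ICC 0.01 | 0.05 | 0.10 | 0.20 |
|---|---|---|---|---|
| R33 Activity, SING only | 5.2% | 5.6% | 6.1% | 7.3% |
| R33 Activity, two active arms | 5.2% | 6.2% | 7.5% | 9.8% |
| R33 Activity, all four arms | 5.4% | 7.5% | 9.9% | 14.7% |
| R61 paired t-test | 5.4% | 7.2% | 9.7% | 14.3% |

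Ownership is within 0.3 points of Activity.

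**3. Error of tests that respect the grouping.** In R61, a t-test on the 10 group means (9 df) gave 4.9–5.0% at every ICC, also with 45 or 40 completers lost at random. A random intercept with 9 df gave 2.2–4.3%. In R33, a random intercept with 36 df (40 groups minus 4 arms) gave 3.7–5.1% for Activity under all three patterns, about 3.7% at ICC 0. For SING versus karaoke with unequal group variances at ICC 0.05 to 0.20, a common group variance gave 4.6–8.1% and arm-specific variances 4.7–5.0%.

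**4. Power of those tests.** The variance of the R61 mean, in SD² units, is [ICC + (1 − ICC)/5]/10. With all arms correlated, the R33 Activity contrast has the same variance. At ICC 0.05 it is (0.05 + 0.19)/10 = 0.024, so an effect of 0.5 SD has noncentrality 0.5/√0.024 = 3.23. Noncentral t gives 82% on 9 df and 88% on 36 df. The SING-only row is simulated (40,000 trials per cell).

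| Power at 0.5 SD, no dropout | ICC 0 | 0.01 | 0.05 | 0.10 | 0.20 | Planned test, independence |
|---|---|---|---|---|---|---|
| R61, group means | 88% | 87% | 82% | 76% | 65% | 93% |
| R33 Activity, all arms correlated | 93% | 92% | 88% | 83% | 73% | 94% |
| R33 Activity, SING only correlated | 93% | 93% | 92% | 91% | 88% | 94% |

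With dropout at ICC 0.05, R61 power is 79% with 45 completers and 75% with 40 if losses are even across groups, or 78% and 73% if they are random. R33 power with all arms correlated is 85% with 180 completers and 80% with 160.

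The R33 effect of 0.5 SD is assumed, since the documents give no between-arm effect. If only SING differed from the other arms by 0.5 SD, the Activity main effect would be 0.5/2 = 0.25 SD, and power about 41% at ICC 0 and 35% at ICC 0.05 (all arms correlated).

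**The case against.** The strongest reply is that nothing in the documents supports any particular ICC. Outcomes are measured on individuals: tasks set to personal thresholds, model parameters fitted per person, separate interviews. Noise in those estimates would pull the ICC of change down. The errors above 14% need an ICC of 0.20, and in R33 they need it in all four arms, two of which involve quiet listening. That stands. The omission is certain, its size is not, and the lower ICC columns deserve most weight. It is still an argument for a test that is valid whatever the ICC.

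Second, few decisions depend on it. Metrics go forward to R33 only if they "change by two standard deviations or more from baseline pre-intervention", which is not a p-value, and R33 is described as mechanistic rather than an efficacy trial. The first part stands: the Go/No-Go rule is not directly affected. The second does not remove the problem, because R33 still draws inferences about active ingredients from its tests.

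Third, the Inclusion/Exclusion section requires medication type and dose as a covariate in all analyses, and a test on group means has no place for a participant-level covariate. Neither does the planned paired t-test; a random-intercept model does. The figures here ignore the covariate.

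Fourth, facilitator effects are not modelled and the number of facilitators is not stated. That stands too: the all-arms case is an upper case only for which arms are correlated, not for every source of dependence.

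**Conclusion.** The concern holds and should be fixed. Both phases deliver the intervention in fixed groups of five, and neither the tests nor the sample size takes account of it. Under any positive within-group correlation the planned tests are too liberal. For R33 Activity, true error is 5.2–5.4% at ICC 0.01 and 5.6–7.5% at 0.05, rising to 7.3–14.7% at 0.20, depending on which arms are correlated. The ICC values are assumptions; at zero there is no inflation. The consequence lies mainly in the R33 Activity and Ownership tests. R61 p-values are affected in the same way, but its Go/No-Go threshold is not directly affected.

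**What to change.** **R33.** Keep the 2x2 model of pre-post change (Activity, Ownership, interaction). Add a random intercept for session group nested in arm, with small-sample degrees of freedom (about 36 for arm contrasts). Include the medication covariate the protocol already requires. As a sensitivity analysis, let the group variance differ by arm. Replace the reused 31 with power for the between-arm contrasts, with clustering, over a range of effects and ICCs.

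**R61.** Test the mean pre-post change on the 10 group means (9 df). A random intercept for group is the alternative and can carry the medication covariate, but it is conservative on 9 df. Restate power for the 50 planned participants under the chosen test, over an ICC range that includes values near zero and with the expected dropout. Do not simply restate the sample size as 31 × (1 + 4 × ICC), because that ignores the loss to 9 df.

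**Cost.** Analysis wording and a few lines of code. No new patients or data are needed, since session group is known from scheduling. The price is lower stated power, some of it lost even at ICC 0 (at 0.5 SD, R61 falls from 93% to 88% and R33 Activity from 94% to 93%), and a slightly conservative R33 test when the ICC is zero.

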- (3) **Karaoke** (Activity +/ Ownership -, n=50). The trained facilitator will provide a microphone and speaker along with a karaoke playlist of music and a screen to view lyrics. In the first 10 minutes, participants will be encouraged to write down a list of songs that they would like to sing to. The list can be edited at any point. For 5 minutes, they will conduct body and vocal warm ups, listening to self and others. For 90 minutes, the facilitator will order the participants in turn and invite them to perform karaoke at 60-75 decibels. Each participant will be encouraged to participate. For the final 15 minutes, the session will be concluded, and if the final session, participants will be informed of local opportunities to engage further with music making and musical experiences.

[figure not shown]

Figure 7. Behavioral simulation across three iterations of the HGF. 1) (top panel) standard HGF implementation; 2) (middle panel) adding Nu, which codes the weighting between sensory evidence and perceptual beliefs; 3) (bottom panel) allowing a more flexible influence of Nu on the overall model. Simulated responses were then compared with observed behavior, comparing the proportion of identical responses (left), individual phi coefficients (middle), and proportion of “yes” responses (right).

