Participants will receive a comprehensive psychological assessment during the course of this study, and feedback will be provided to participants about their mental health. If the participant chooses, they may request that this diagnostic information be provided to their clinician at CMHC or to other clinicians, at no charge to the patient, which may help to enhance the quality of care they receive. If the participant does not wish to have this information released to their clinician, it will of course be kept confidential. Participants who are not already in treatment will be provided with referrals to mental health professionals as needed, which may help them to gain access to treatment that they would not otherwise receive. In terms of benefits to society, we hope that this study will increase our understanding of the processes through which music confers health benefits.

SECTION VI: RESEARCH ALTERNATIVES AND ECONOMIC CONSIDERATIONS

1. **Alternatives:** *What other alternatives are available to the study subjects outside of the research?*

The alternative is not to participate.

2. **Payments for Participation (Economic Considerations):** *Describe any payments that will be made to subjects, the amount and schedule of payments, and the conditions for receiving this compensation.*

Participants can be compensated \$100 for each visit of the seven visits, for a total of \$700.

We can compensate up to \$50 in transportation studyper visit as necessary to help people attend.

3. **Costs for Participation (Economic Considerations):** *Clearly describe the subject's costs associated with participation in the research, and the interventions or procedures of the study that will be provided at no cost to subjects.*

There are no costs associated with participation in this research. The assessments included in this study will be provided to the participants at no cost. The CMHC, where the study will occur, is a short walk from areas where participants may receive medical care and is accessible by public transportation from areas throughout New Haven County.

4. **In Case of Injury:** *This section is required for any research involving more than minimal risk, and for minimal risk research that presents the potential for physical harm (e.g., research involving blood draws).*

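### Information on outside music opportunities is given at session four in R61 and in every R33 arm, ahead of the outcome tests and with no stated interval: a small but avoidable route of contamination

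*Combined protocol and SAP*

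**What the plan says.** **Information given in session four**
- R61 (Section I, item 4, SING Intervention): in the last session, "participants will be provided with information sheets on local studio opportunities, karaoke nights and other opportunities to produce, perform and experience music".
- R33 arm (1), listening without ownership (Section I, item 13, R33 Phase): the facilitator ends by "sharing follow-up music opportunities at the end of the fourth and final session".
- R33 arm (2), listening with ownership: "If it is the final session, they will be offered follow-up information about the musical opportunities".
- R33 arm (3), karaoke: "if the final session, participants will be informed of local opportunities to engage further with music making and musical experiences".
- R33 arm (4), SING: "information sheets on local studio opportunities, karaoke nights and other opportunities to produce, perform and experience music".

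**Outcome timing.** Section I, item 4 places the R61 tasks and interview "prior to and following the full SING intervention". The R33 tasks are likewise repeated after the assigned condition. Neither phase states how many days separate session four from the post-test. No visit schedule is printed. The only count is in Section VI, item 2, which pays "for each visit of the seven visits".

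**Related provisions.** Both listening arms are told during sessions to listen silently. Item 4 also says that access to music after the group ends is important to offer. No passage holds the information back until testing is finished.

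**The concern.** Activity is one of the two factors that R33 is built to separate, and the plan guards it inside the sessions by asking the listening arms not to sing. The study then points the same people towards further music before their outcome is measured. Anyone in a listening arm who starts making music in that interval gains some active exposure, which may pull the Activity contrast towards zero.

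R61 has no control group, and its Go rule rests on change from baseline. Music-making between session four and the post-test would be counted as change due to SING. Analysis cannot separate the two afterwards unless outside activity is recorded in a usable form.

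**Working it through.** **1. Order of events.** In all five descriptions the information belongs to the last session. The tasks come after the intervention. The information therefore precedes the post-test, by an unknown interval.

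**2. Is there a gap?** The breakdown of the seven visits is not printed, and more than one fits:
- 1 screening + 1 baseline + 4 sessions + 1 post-test = 7, which leaves a gap.
- 1 screening + 1 baseline tasks + 1 baseline interview + 4 sessions = 7, with the post-test on the day of session four and almost no gap.

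The first is more natural. The test battery is long: 12 blocks × 30 trials = 360 trials for conditioned hallucinations, a 120-trial social task with a confederate meeting and practice, and in R61 an in-depth interview. Adding this to a two-hour session is unlikely, but the protocol does not exclude it.

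**3. What the plan's 0.01 measures.** Item 13 gives a difference of 0.01, an SD of 0.02, two-sided 0.05, 80% power and at least 31 participants, in both phases. The paired normal approximation gives

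n = ((1.960 + 0.842) × 0.02 / 0.01)² = 5.604² = 31.4,

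which agrees with 31. A two-group comparison with the same inputs needs 63 per group. So 0.01 is the pre-to-post change within SING patients, as the text also says. The documents give no value for the Activity contrast.

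**4. Direction and size of the effect on the Activity contrast.** Let D be the true contrast. Let c_L and c_A be the shares taking up outside music-making before the post-test in the listening and active arms, and g_L and g_A the gain per person who does so. Then

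observed contrast = D + c_A·g_A − c_L·g_L.

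- Equal uptake and equal gains: the terms cancel and the contrast stays at D.
- Active arms gain nothing further (g_A = 0) and listening-arm takers gain a fraction f of D: the contrast is D(1 − c_L·f).
- Higher uptake or gain in the active arms: the contrast could widen. The SING sheet is the more specific one, so this cannot be ruled out.

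None of these quantities is in the documents. As an assumption only, take c_L from 10% to 30%. With f = 1, the proportional loss is 10% to 30%. With f = 0 it is nil. The value f = 1 is a ceiling, since it credits outside music in a short interval with the full Activity effect of four two-hour facilitated sessions.

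**5. What is recorded.** The R61 Aim 3 interviews ask about participants' relationship with music, now and in the past. Only the group-experience topic is restricted to the post-intervention interview, so the music topic appears in both. It is qualitative and not tied to the interval before testing. No such interview is described for R33.

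**The case against.** The strongest reply has five parts.

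- **The gap is inferred.** This stands. If testing is on the day of session four, the point has no practical effect.
- **Karaoke is not promoted to the listening arms.** This stands. A reader might infer that staff send listening-arm participants to karaoke, itself an R33 arm. The documents do not support that: karaoke nights and studios are named only for SING, in R61 and in R33 arm (4). The listening arms get unspecified opportunities, which could be for listening.
- **Outside music is already asked about.** This stands in part: true for R61, qualitatively, and not described for R33. It would be wrong to say that the plan collects nothing.
- **All arms are informed, so the effect cancels.** This holds only if uptake and gains are similar across arms. The active arms have already had the active ingredient and may gain less, and the wording differs between arms.
- **The timing is deliberate, and outside music is unrestricted during the four weeks anyway.** Both are true. Continued access is a stated aim, but it does not require the sheet to come before testing. Moving it closes only one route, though it is the one the study itself creates.

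For R61, the Go rule needs a change of two standard deviations, and nothing shows that a short spell of outside music would move a metric that far.

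**Conclusion.** The point holds as a statement of what the plan permits. In both phases the study draws attention to outside music before the outcome is measured, and sets neither a delay nor a post-test window. The R33 Activity contrast could shrink, and the R61 change could include exposure that is not SING. This rests on two assumptions: that there is a gap before the post-test, and that some participants act on the information by making music. For shrinkage in R33, the listening arms must also gain more from it than the active arms.

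The size is unquantified and probably small. A reader might apply the 10% to 30% illustration to the plan's figure and report an Activity contrast falling from 0.01 to 0.009–0.007, with power falling from 94% to 89%–70% at 100 versus 100. The documents do not support this: 0.01 is the pre-to-post SING change, the uptake is assumed, and full benefit from brief outside music is a ceiling.

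Severity is minor and confidence moderate. The case for acting rests on the very low cost, not on a demonstrated loss.

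**What to change.** In Section I, item 4 (SING Intervention, R61) and item 13 (R33 Phase, arms (1) to (4)):

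1. Move the information from session four to the end of the post-intervention assessment, after all tasks and the interview.
2. Use one identical sheet in every arm.
3. Send it to anyone who misses that visit, so that continued access is kept.
4. Optionally, in both phases, add one structured post-test question on music-making outside the study since baseline. This covers the four weeks of sessions as well as the interval after them, and supplements the qualitative R61 interview.

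The cost is a wording change in the protocol and the manuals, plus one question if the option is taken. Participants receive the sheet one visit later. No extra visits, staff or participants are needed.
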